4.1.4 Selection and timing of doses for each patient

Prior to inclusion of a new patient in the phase I part the investigator has to confirm the actual dose tier of BI 6727 for the patient with the clinical monitor of the sponsor who oversees the dose escalation steps according to the safety data of patients from all trial sites.

BI 6727 will be administered as an intravenous infusion under the supervision of the investigator or designated personnel. Subcutaneous cytarabine injections will be administered according to the SPC.

The trial drugs may be administered at any time during the day. In case the second dose of BI 6727 is missed for administrative reasons the respective dose will be administered on the following two days. In case a dose of cytarabine is missed for administrative reasons the respective dose will not be administered at a later time (any missed cytarabine dose must be documented in the eCRF).

At the end of each treatment cycle, the response to treatment will be assessed. To continue treatment with further cycles, the following criteria must be met:

- 1.) Absence of disease progression (see [section 5.1.1](#))
- 2.) Neutrophils $\geq 500 / \mu\text{L}$ ($0.5 \times 10^9 / \text{L}$) and platelets $\geq 25,000 / \mu\text{L}$ ($25 \times 10^9 / \text{L}$); unless CTCAE grade 4 neutropenia or thrombopenia was preexistent
- 3.) Acceptable tolerability (in case of DLT, patients may continue therapy only after recovery from DLT to CTCAE levels which allow further therapy and only with a reduced dose), and recovery from drug-related cardiac toxicity.

In case criterion 2 is not fulfilled, the peripheral blood should be re-evaluated for up to three weeks. As soon as criterion 2 is met the treatment should be continued (unless other criteria for discontinuation or withdrawal apply, see [section 6.3](#)). A delay of haematopoietic reconstitution (i.e criterion 2 unmet) for more than three weeks after the end of the treatment cycle qualifies for DLT in patients with CRi or PR (see [section 5.2.3](#)). Any case of a delay in treatment cycle should be communicated to the clinical monitor of Boehringer Ingelheim. Progressive disease will lead to discontinuation of treatment.

Administration of the trial drugs has to be stopped temporarily in case of a DLT (see [section 5.2.3](#)). Patients may continue therapy only after recovery from the DLT to CTCAE levels which allow further therapy and only with a reduced dose of BI 6727, the LD-Ara-C dose will remain unchanged. The new dose of BI 6727 must be finally agreed on between the clinical monitor of Boehringer Ingelheim and the investigator. The reduced dose will be valid for all following treatment cycles in the individual patient. A reduction of the dose will be allowed only once for an individual patient during the whole trial. In case, a patient experiences a second episode of DLT with the reduced BI 6727 dose, the treatment has to be

permanently discontinued. Likewise, treatment has to be discontinued in case the DLT is not reversible.

In this trial, an intrapatient dose escalation of BI 6727 will be allowed in the phase I part of the trial to increase the probability of clinical benefit. In case of a clinical response other than CR or CRI (i.e. PR or no change), the patient may receive a higher dose of BI 6727 provided that the drug is tolerated well (i.e. non-haematological drug related adverse events CTCAE grade ≥ 2 and haematological drug related adverse events CTCAE grade ≥ 3 unless preexistent). The BI 6727 dose escalation may be up to 50 mg/administration for both schedules. All decisions on intrapatient dose escalation will be made only in agreement between the investigator and the sponsor. Beginning after the first cycle of treatment, dose escalations may be repeated after every cycle and may in individual patients exceed the MTD found in this trial. A dose escalation must not be performed in patients who have achieved CR or CRI.

All changes of the BI 6727 dose will simultaneously affect both days of BI 6727 administration, i.e. BI 6727 dose will always remain the same on days one and fifteen.

4.1.5 Blinding

This phase I / IIa trial will be performed according to an open design. Although a double-blind double-dummy design would be feasible, this would necessitate additional placebo-infusions/injections which are considered dispensable in this phase I/IIa exploratory trial in these highly compromised patients. Without placebo-infusions/injections, the obvious difference in treatment schedules precludes blinding of both the patient and the investigator. Therefore, no blinding is done. For similar technical reasons, the statistical analyses will be performed in an open fashion.

This open-label trial will also be handled in an open fashion by the sponsor throughout. The eCRF will contain information on randomised treatment.

4.1.6 Packaging, labelling, and re-supply

BI 6727 will be supplied in 100 mL vials containing 200 mg BI 6727 OR in 175 mL vials containing 350 mg BI 6727.

Ara-C will be supplied in vials containing cytarabine at a concentration of 20 mg/ml.

BI 6727 will be labelled with trial number, medication number, quantity of dosage units and strength, identification code, pharmaceutical dosage form, route and mode of administration, term 'for clinical trial use' (domestic language), sponsor name and address, storage conditions, use-by-date.

In the phase I part of the trial cytarabine will be dispensed with the commercially available label and an additional label indicating trial number, medication number, term 'for clinical trial use' (domestic language) and sponsor name.

In the phase II part of the trial cytarabine will be supplied in 2 ml vials containing 40 mg cytarabine. Cytarabine will be labelled with trial number, medication number, quantity of

dosage units and strength, identification code, pharmaceutical dosage form, route and mode of administration, term 'for clinical trial use' (domestic language), sponsor name and address, storage conditions, use-by date. The cytarabine dispensed for the phase I part of the trial might be used - if still available - in phase II part as well.

Examples of the labelling of the medication are included in the ISF.

Medications will be delivered to the investigator's pharmacy where the total dose per patient will be prepared upon request from the investigator.

For preparation of the BI 6727 infusion solution, the preconcentrate of BI 6727 will be diluted in 0.9% sodium chloride. The maximum concentration of BI 6727 in the ready-for-use infusion must not fall below 0.02 mg/mL nor exceed 1.0 mg/ml. The content of several vials may be needed for administration of the requested dose. For further details, please refer to the ISF.

Cytarabine will be prepared and handled according to the package insert and the SPC provided by the manufacturer.

Please refer to section 8.2.1 for drug accountability.

4.1.7 Storage conditions

BI 6727 and cytarabine have to be stored in the original packaging in the hospital pharmacy in a limited access area at the temperature indicated on the trial drug label.

For more details on BI 6727, please refer to the IB (c01694302-14) and the ISF. For more details on cytarabine, please refer to the SPC.

4.2 CONCOMITANT THERAPY

4.2.1 Rescue medication and additional treatments

Rescue medication to reverse the action of BI 6727 or cytarabine is not available. Potential side effects of BI 6727 and cytarabine have to be treated symptomatically. Patients should receive supportive care according to local guidelines regarding blood product support, antibiotics, analgesics, skin and mouth care etc. The use of growth factors such as granulocyte colony stimulating factor (G-CSF) will be allowed, but growth factors should be avoided in the first treatment cycle for better assessment of safety and response parameters. Treatment with corticosteroids will be allowed. All treatments have to be recorded in the eCRF with duration.

All concomitant non-antileukaemia therapies to provide adequate care may be given as clinically necessary but should be recorded in the eCRF except for vitamins or nutrient supplements.

Trade name, indication and dates of administration of concomitant therapies will be documented. The use of prophylactic antiemetic drugs should be documented. For parenteral

nutrition during the trial, the components need not to be specified in detail. It should just be indicated as 'parenteral nutrition'. If a patient needs anaesthesia, it will be sufficient to indicate 'anaesthesia' without specifying the details.

4.2.2 Restrictions

During the trial, no additional chemo- or immunotherapy will be allowed.

For patients included in the phase I part of the trial (relapsed/refractory AML) prior cytotoxic antileukaemia chemotherapy (except hydroxyurea) or antileukaemia immunotherapy must have been discontinued at least two weeks before the first administration of the trial drug and the patient must have recovered from all clinically relevant reversible toxicities. For any other prior investigational treatment, a time interval of the investigational drug's half-life x5 must have elapsed from the last administration of the other investigational drug to the first administration of BI 6727.

For patients included in the phase IIa part of the trial (previously untreated AML) no prior chemo- or immunotherapy for AML is allowed (except hydroxyurea) before the administration of the trial drugs.

For peripheral blast control, hydroxyurea may be given until one day before the first administration of the trial drug in all patients. The start date, end date, and dose will be recorded in the e-CRF.

Concomitant therapy with other investigational drugs will not be allowed during the trial.

4.3 TREATMENT COMPLIANCE

BI 6727 will be administered as an intravenous infusion under the supervision of the investigator or designated personnel. Subcutaneous cytarabine injections will be administered according to the SPC. The investigator or his/her deputy will check at visits 2, 3 and 4 whether the patient has received the cytarabine medication according to the protocol on the scheduled previous days until day 10. Any discrepancies will be explained in the CRF by the investigator or his/her deputy.

The plasma concentrations of the trial drugs will be determined.

5. OBSERVATIONS

5.1 EFFICACY - PHARMACODYNAMICS

The efficacy endpoints will be assessed at the time points specified in the flow charts. The primary endpoint for efficacy is response. Secondary endpoints for efficacy are event free survival, relapse free survival, remission duration, overall survival.

5.1.1 Assessment of response

Response will be assessed in the peripheral blood and in the bone marrow. In case of extramedullary manifestations of leukaemia, assessment by imaging will complement the blood and bone marrow assessment of response.

The baseline bone marrow assessment should be done within 2 weeks prior to start of treatment with the trial drugs.

The first response assessment in the bone marrow will be performed at the end of the first treatment cycle. The classification of response is defined below.

Response assessment after further treatment cycles will be performed in a two step fashion to reduce patient stress:

- ! First, the manifestation of leukaemia will be assessed clinically and in the peripheral blood. In case of persistence of leukaemia cells in the blood no bone marrow aspiration must be performed.
- ! If leukaemia cells cannot be detected in the peripheral blood and other clinical signs of active leukaemia are absent, a bone marrow aspirate will be obtained before the next treatment cycle.
If the bone marrow demonstrates CR or CRi, further bone marrow examination will be performed after every other treatment cycle.
In case of persistence of leukaemia in the bone marrow and continuing absence of leukaemia in the peripheral blood, further bone marrow examination will be performed after each treatment cycle to earlier detect CR or progressive disease.
- ! A bone marrow examination should be performed as soon as possible when progressive disease or relapse after CR or CRi is suspected.

After approval of Protocol Revision I, bone marrow aspirations and disease assessments only have to be done per local standard of practice to support the decision on further treatment with volasertib. These efficacy data will not be entered in the eCRF; documentation in the source data is sufficient.

5.1.1.1 Definition of response

Response to treatment will be evaluated according to the following criteria (modified from the National Cancer Institute/Cancer and Leukemia Group B criteria, R06-0452):

- ! Complete remission (CR)
morphologically leukaemia free state (i.e. bone marrow with < 5% blasts by morphologic criteria and no Auer rods, no evidence of extramedullary leukaemia) and absolute neutrophil count $\geq 1,000/\mu\text{L}$ and platelets $> 100,000/\mu\text{L}$.
- ! Complete remission with incomplete blood count recovery (“incomplete” CR, CRi)
All of the above criteria for CR must be met, except that neutrophils $< 1,000/\mu\text{L}$ or platelets $< 100,000/\mu\text{L}$ in the blood.
- ! Partial remission (PR)
All of the above criteria for CR must be met, except that the bone marrow contains $\geq 5\%$ but less than 25% blasts (or $\leq 50\%$ of initial blast count), or < 5% blasts in the presence of Auer rods or abnormal morphology.
- ! No change
Patient survives ≥ 7 days following completion of initial treatment cycle with persistent leukaemia in the last peripheral blood smear or bone marrow ($>25\%$ blasts), or with persistent extramedullary disease, but without further clinical deterioration due to leukaemia or increase of blast population in the bone marrow or peripheral blood.
- ! Progressive disease (PD)
Patient survives ≥ 7 days following completion of initial treatment cycle with increase of blast population in the bone marrow or peripheral blood or aggravation or new development of extramedullary disease or further deterioration or death due to leukaemia. Patients with a global deterioration of health status requiring discontinuation of treatment without objective evidence of pd at that time should be classified as having ‘symptomatic deterioration’. Every effort should be made to document the objective pd even after discontinuation of treatment.
- ! Aplasia
Patient survives ≥ 7 days following completion of initial treatment cycle, then dies while cytopenic, with the last post-treatment bone marrow aplastic or hypoplastic (i.e. $<20\%$ cellularity) and without leukaemia blasts.
- ! Indeterminate
(a) Patient survives < 7 days after completion of initial treatment cycle; or (b) patient survives ≥ 7 days following completion of initial treatment cycle, then dies with no persistent leukaemia in the peripheral smear but no post-treatment bone marrow examination or (c) patient does not complete the first cycle
- ! Recurrence (relapse)
after CR reappearance of leukaemic blasts in the blood or $> 5\%$ blasts in the bone marrow not attributable to any other cause.

Patients with the response status “aplasia” or “indeterminate” will be treated as non-responders for primary statistical analyses of efficacy parameters.

5.1.2 Event Free Survival

Event free survival (EFS) is defined for all patients that entered the trial, and measured from the date of randomisation to the date of disease progression (treatment failure), relapse or death from any cause, whichever occurs first (R06-0452).

5.1.3 Relapse-free survival

Relapse free survival is defined only for patients who achieve CR, and is measured from the date of attaining CR until the date of disease recurrence or death from any cause, whichever occurs first.

5.1.4 Remission duration

Remission duration analysis is defined only for patients who achieve CR, and is measured from the date of attaining CR until the date of disease recurrence (relapse). For patients who die without report of relapse, remission duration will be censored on the date of death, regardless of cause.

5.1.5 Overall survival

Overall survival (OS) is defined for all patients that entered the trial, and measured from the date of randomisation until death from any cause.

5.2 SAFETY

5.2.1 Adverse events

Upon inclusion into the trial, the patient's condition is assessed (e.g. documentation of history / concomitant diagnoses and diseases), and all relevant changes from baseline are noted subsequently.

Patients will be required to report spontaneously any adverse events (AEs) as well as the date of onset and end of these events. These include all events that affect the well-being of the patients irrespective of their relatedness to the treatment. Specific questions will be asked whenever required or useful to more precisely describe an AE and to allow a grading according to the CTCAE criteria (version 3, [R04-0474](#)).

A carefully written record of all AEs has to be kept by the investigator in charge of the trial. Records of AEs will include data on the date of onset, end date and CTCAE grading of the event as well as any treatment or action required for the event and its outcome.

The events leukopenia, neutropenia, thrombocytopenia are expected after treatment with BI 6727 and will be considered as listed events for regulatory purposes (see IB for details, [c01694302-14](#)). The events listed in the SPC are expected after treatment with cytarabine.

AEs with onset within 21 days after the last trial drug administration in the last treatment cycle will be considered as on treatment. All AEs, including those persisting after trial completion must be followed up until they have resolved or have been sufficiently characterised or the clinical monitor and the investigator agree to not further pursue them.

All events, serious and non-serious, with onset within six weeks after the last application of the trial drug (observational phase) must be reported. All events, serious and non-serious, that are considered related to the trial drugs must be reported irrespective of the time of onset.

Deaths (unless they are considered drug-related or trial related) will not be reported as serious adverse events if occurring later than six weeks after last administration of the trial drugs, since death will be followed-up separately (secondary endpoints).

Definitions and requirements for documentation and reporting of AEs and serious adverse events (SAEs) during the trial are provided in Section 8.4.1.

Patients may be hospitalised for administrative reasons during the trial (e.g. days on which infusion of the trial drug takes place). These and other hospitalisations planned at the beginning of the trial will not be considered as SAE if they have been reported at the screening visit in the eCRF and performed as planned.

Changes in safety tests including blood pressure, pulse rate, electrocardiogram (ECG) and laboratory tests will be recorded as AEs, if they are not associated with an already reported AE, symptom or diagnosis, and:

- ! 'action is required and taken with the investigational drug, i.e. dose reduction or treatment discontinuation,'
- or
- ! 'treatment due to the event is required (i.e. a concomitant medication is added or changed).

5.2.2 Worsening of pre-existing conditions

Expected fluctuations or expected deterioration of the underlying disease will not be recorded as an AE. If progressive disease occurs and is associated with symptoms, the signs and symptoms of progressive disease will be reported as an adverse event or a serious AE (if applicable).

Worsening of other pre-existing conditions will be recorded as an AE or SAE if one of the following criteria is met:

- ! the criteria for an SAE apply,
- ! 'action is required and taken with the investigational drug, i.e. dose reduction or treatment discontinuation,
- ! 'treatment is required, i.e. concomitant medication is added or changed,
- ! the investigator believes a patient has shown a clear, unexpected deterioration from the baseline condition.

Pre-existing conditions are not recorded as AEs if they do not meet at least one of the above criteria. Specifically, the following will not be recorded as an AE:

- ! 'pre-existing conditions present at baseline, which remain unchanged during the trial,
- ! 'expected fluctuations or expected deterioration of a pre-existing condition.

5.2.3 Dose limiting toxicity

Dose limiting toxicity (DLT) is defined as drug related CTCAE grade ≥ 3 non-haematological toxicity (excluding: untreated nausea, untreated vomiting, CTCAE grade 3

untreated diarrhoea, CTCAE grade 3 "febrile neutropenia" and CTCAE grade 3 "infection with grade 3 or 4 neutrophils").

In patients with CRI or PR, persistent CTCAE grade 4 neutropenia or thrombocytopenia until three weeks after the end of the treatment cycle will be regarded a DLT unless the respective grade 4 cytopenia was pre-existent. In patients who required platelet substitution to maintain a CTCAE grade < 4 before treatment, a CTCAE grade 4 thrombocytopenia after treatment does not constitute a DLT.

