4.1.3 Selection of doses in the trial

Two treatment schedules will be investigated in the phase I part of the trial to determine the MTD. All patients will receive either BI 6727 on days 1 and 15 either as monotherapy or in combination with LD-Ara-C (2 x 20 mg/d on days 1-10) in 28-day cycles. The starting dose of BI 6727 in treatment schedule A is 150 mg and corresponds to 50 % of the recommended Phase II dose of 300mg and 38% of the MTD of 400mg that has been determined in a phase I monotherapy dose escalation trial to be well tolerated.

To determine the MTD (for definition see 5.2.4), dose escalation for BI 6727 will be conducted following the “3 + 3 design with de-escalation” ([R04-0569](#)). A cohort of three patients will be treated at the starting dose level and observed until the end of the cycle. The dose level will be escalated with each new cohort until at least one out of three patients of a cohort experiences DLT (for definition see [section 5.2.3](#)). If one patient experiences a DLT, then three additional patients will be treated at the same dose level; if none of the three additional patients experiences a DLT, then the dose escalation will be continued by treating the next cohort of three patients at the next higher dose level. If at least two out of up to six patients at a dose level experience a DLT, the MTD has been exceeded and the dose will be deescalated until a dose level is reached in which at most one DLT out of six patients is observed ([R01-0028](#)). A dose step for escalation shall not exceed 50 mg/administration, a dose step for de-escalation shall not exceed 50 mg/administration.

The starting of BI 6727 for dose escalation in schedule B will be the dose determined as BI 6727 MTD in schedule A.

The dose of the trial drug on days one and fifteen will always remain the same (i.e. simultaneous and equal dose escalation for days one and fifteen). The dose of cytarabine remains always unchanged.

In case two or more cases of DLT are observed at the starting dose of 150 mg either in monotherapy or in combination with LD-Ara-C the dose BI 6727 will be deescalated to a lower dose cohort as outlined above.

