5.2.4 Maximum tolerated dose

The MTD is defined as the highest dose at which six patients have been treated and less than two patients experienced DLT within the first cycle of treatment. The MTD will be defined based on safety data from the first cycle only. However, the data from later treatment cycles will be considered for future development of BI 6727 in this indication. To determine the MTD of BI 6727 on days 1 + 15 in combination with LD Ara-C (schedule A), the dose escalation starting with 150 mg BI 6727 will be conducted following the "3 + 3 design with de-escalation" as described in [section 4.1.3](#). To determine the MTD of BI 6727 on day 1 + 15 monotherapy (schedule B), the dose escalation starting with the BI 6727 MTD determined in schedule A will be conducted following the "3 + 3 design with de-escalation" as described in [section 4.1.3](#).

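### At any one assessment the PR branch of the haematological DLT rule is empty, because PR as defined requires recovered blood counts

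*Protocol*

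**What the plan says.** - **DLT rule, Protocol 5.2.3.** The haematological DLT reads "In patients with CRI or PR, persistent CTCAE grade 4 neutropenia or thrombocytopenia until three weeks after the end of the treatment cycle". It does not apply if the same grade 4 cytopenia existed before treatment. Thrombocytopenia does not count in patients who already needed platelet substitution.
- **Same rule, Protocol 4.1.4.** Re-treatment criterion 2 requires neutrophils of at least 500/µL and platelets of at least 25,000/µL, and the protocol ties these limits to grade 4. If they are missed, "In case criterion 2 is not fulfilled, the peripheral blood should be re-evaluated for up to three weeks". Failure to recover "for more than three weeks after the end of the treatment cycle qualifies for DLT in patients with CRi or PR".
- **Response, Protocol 5.1.1.1.** CR needs neutrophils of at least 1,000/µL and platelets above 100,000/µL, and CRi waives the counts. For PR, "All of the above criteria for CR must be met, except that the bone marrow contains" 5% to under 25% blasts (or at most half the initial blast count), or under 5% with Auer rods or abnormal morphology. *No change* needs "persistent leukaemia in the last peripheral blood smear or bone marrow" (above 25% blasts), or persistent extramedullary disease.
- **Use of the DLTs.** Section 5.2.4: "The MTD will be defined based on safety data from the first cycle only". Section 4.1.3: "If at least two out of up to six patients at a dose level experience a DLT, the MTD has been exceeded".
- **Data source.** SAP 5.2.6 identifies DLTs from an eCRF question. SAP 5.1.2 uses the investigator's response assessment, without central review or a check against marrow measurements.

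**The concern.** The DLT rule names two response groups, but the PR definition brings in blood counts that rule out the toxicity being looked for. Only CRi sets the counts aside.

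This matters because the sentence is the only DLT criterion for cytopenia itself; the rest of section 5.2.3 concerns non-haematological toxicity. Section 1.2.1 reports neutropenia and thrombocytopenia as the dose limiting toxicity in the earlier phase I trial, and section 1.4 expects overlapping toxicity from cytarabine.

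The MTD is the phase I primary endpoint. The schedule A MTD is also the starting dose for schedule B and, unless another dose is recommended, the dose for 43 phase IIa patients. For the individual patient, a DLT means that BI 6727 may be resumed only at a reduced dose; an uncounted event does not.

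**Working it through.** **1. The plan's own DLT figure.** Table 7.6: 1 gives the probability of two or more DLTs in six patients, which is 1 − (1−p)^6 − 6p(1−p)^5. For p = 0.40, 0.42 and 0.45 this gives 0.7667, 0.7965 and 0.8364, matching the stated 0.77, 0.80 and 0.84. The table is not in dispute; the issue is which events enter the count.

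**2. The limits side by side.**

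| | Needed for PR (5.1.1.1) | Grade 4 / criterion 2 missed (4.1.4) | Ratio of limits |
|---|---|---|---|
| Neutrophils | ≥1,000/µL | <500/µL | 1,000/500 = 2 |
| Platelets | >100,000/µL | <25,000/µL | 100,000/25,000 = 4 |

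PR needs both counts recovered, while either cytopenia alone is enough for the DLT. The ranges do not overlap.

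**3. Enumeration.** The definitions were applied to a grid of neutrophils 0–3,000/µL, platelets 0–200,000/µL, eight blast percentages from 2 to 30, and Auer rods present or absent. Combinations that also met grade 4 cytopenia were 0 of 41,000 for PR and 6,570 of 16,240 for CRi. These are grid cells, not patients. The grid left out abnormal morphology and the half-of-initial-blasts option; both concern marrow only, so they cannot create an overlap in counts.

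**4. Timing in cycle 1.** Response is first assessed at the end of cycle 1, and the re-evaluation window then runs to about day 28 + 21 = day 49. A patient whose counts satisfy PR also satisfies criterion 2 and would normally go on to cycle 2. Two routes to the PR branch remain:
- Counts fall to grade 4 after the response assessment and before the next cycle. The marrow may be taken up to 3 days early and visit 7 may be up to 3 days late, so the two dates can differ by some days. This route strains the idea of persistence.
- PR is first reached after the three-week window, once counts recover, and is linked back in retrospect.

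**5. Where the affected patient goes.** Take a surviving patient with 5% to under 25% marrow blasts, no blood blasts, no extramedullary disease, no progression and new lasting grade 4 cytopenia.
- CRi fails on the marrow.
- PR fails on the counts.
- *No change* fails, because marrow blasts are not above 25% and there is no blood or extramedullary disease.
- *Aplasia* fails because the patient is alive and the marrow has blasts. *Indeterminate* fails because the patient completed cycle 1 and survived.

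The event is therefore not a DLT unless the investigator calls PR on marrow alone.

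**6. Effect of one uncounted event under section 4.1.3.**

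| True | Counted | Correct decision | Decision taken |
|---|---|---|---|
| 1/3 | 0/3 | add three patients | escalate |
| 2/3 | 1/3 | MTD exceeded | add three patients |
| 2/6 | 1/6 | MTD exceeded | within the MTD limit |
| 3/3 | 2/3 | MTD exceeded | unchanged |
| 3/6 | 2/6 | MTD exceeded | unchanged |

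**7. Sensitivity on assumed shares.** If the true DLT probability is 0.42 and a share s of DLTs goes uncounted, p becomes 0.42(1−s). For s = 10%, 20%, 30% and 50%, the probability of two or more in six falls from 0.797 to 0.731, 0.654, 0.567 and 0.369. The documents give no value for s, so this is not an estimate for this trial.

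**The case against.** The other side has four good arguments.

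- **Timing.** Section 5.2.3 does not say when the response must be present, so a reader who infers that the PR branch can never apply goes too far. This stands: the two routes in step 4 exist, though both are narrow.
- **Working interpretation.** Two sections tell investigators that a PR patient with unrecovered counts can have a DLT. The natural practice is to judge PR on the marrow, and then no event is lost. This is plausible, and it is probably what was meant. However, nothing in the available text says so, and two investigators could decide differently.
- **Other safety review.** The clinical monitor is the person "who oversees the dose escalation steps according to the safety data of patients from all trial sites", and delayed cycles must be reported to that monitor. Extra marrow samples may be taken to confirm a haematological DLT. Protocol 7.3.3 evaluates duration of neutropenia, and SAP 7.7.2 plots neutrophils and platelets over time. Under Protocol 2.1, 3.1 and 7.3.4 the phase II dose takes account of safety in all cycles, and phase IIa opens only if the risk-benefit assessment stays favourable. These steps weaken the path from one uncounted event to a harmful phase IIa dose. They do not correct the DLT count that defines the MTD.
- **Attribution.** Cytopenia with residual blasts may come from the leukaemia, and deleting PR from the rule would also make the text consistent. That is true, but deletion would drop a group that both sections name.

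**Conclusion.** The definitions conflict. At the same assessment literal PR and grade 4 cytopenia cannot coexist, so in cycle 1 the PR branch is reachable only through narrow timing mismatches. Followed literally, the rule leaves out a kind of event that it appears to name; followed loosely, it may be applied differently between investigators. It should be clarified because it feeds the phase I primary endpoint.

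The frequency, and hence the effect on the MTD, is unknown. The exclusions for earlier grade 4 cytopenia and platelet substitution narrow the group further. What is exact is that one uncounted event can change the decision at 1/3, 2/3 or 2/6.

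A reader might infer that DLTs were missed or that the MTD was set too high. The documents do not support that: they give no patient data, and investigators may have used marrow alone. The conclusion rests on the available text. SAP sections 9.5 and 9.6 and the eCRF wording were not available and may settle part of it.

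**What to change.** Add one sentence to Protocol 5.2.3 and 4.1.4: *For the haematological DLT only, PR is judged on the marrow, blood-blast and extramedullary criteria, irrespective of neutrophil and platelet counts.* Keep the existing exclusions for pre-existing grade 4 cytopenia and prior platelet substitution. Use the same wording in the eCRF DLT question, if it does not already say this. Whether the half-of-initial-blasts option should count for this purpose is for the sponsor to decide; resolving the conflict does not require a change there.

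The cost is one sentence in two places and matching eCRF wording. Counts are already re-evaluated for up to three weeks and a confirmatory marrow is already allowed, so no new sampling is needed. The downside is that some cytopenia due to residual leukaemia may be counted as DLT, which would make the MTD slightly more conservative.
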